### Data analyses

Objective 1: The number and percentage of patients with newly diagnosed MDD initiating treatment with antidepressants will be estimated at 4, 6, 8, 12, and 24 weeks after date of new MDD diagnosis; and the number and percentage of those discontinuing and switching treatment at 4, 6, 8, 12, and 24 weeks following start of antidepressant therapy. They will be reported in tabular form as absolute numbers as well as

	D2.2.3 –Study Protocol for P2 C1-008	
	Author(s): [name], [name]	Version: v3.1 – Final
		Dissemination level: public

proportions, and depicted using Sunburst plots and Sankey diagrams. The statistical analyses will be performed based on OMOP-CDM mapped data using the “TreatmentPatterns” R package.

Objective 2: The duration (mean, median, quantiles 25% and 75%, minimum and maximum) of antidepressant use in patients with newly diagnosed MDD during the first treatment era will be estimated. The index date will be determined as the date of the first prescription of the specific antidepressant class for each individual. Statistical analyses will be conducted using the "DrugUtilization" R package based on OMOP-CDM mapped data.

Objective 3: The number and percentage of patients with newly diagnosed MDD initiating, switching, or discontinuing treatment with psycholeptics) will be estimated at 4, 6, 8, 12, and 24 weeks after the date of treatment initiation with antidepressants; and at 4, 6, 8, 12, and 24 weeks after starting psycholeptics (for switching or discontinuing treatment). This will be reported in tabular form as absolute numbers as well as proportions and depicted using Sunburst plots and Sankey diagrams. The statistical analyses will be performed based on OMOP-CDM mapped data using the “TreatmentPatterns” R package.

For all analyses, results will be reported with a minimum cell count of 5, and any counts smaller than 5 will be reported as <5 to ensure privacy and confidentiality.

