#### B. Secondary research question and objective

Objective:	To estimate the duration of antidepressant use in patients with newly diagnosed major depressive disorder who initiate treatment with antidepressants (NSRIs, SSRIs, or other antidepressants), stratified by age, sex, and country/database during the study period (2013 - 2022)
Hypothesis:	Not applicable
Population (mention key inclusion-exclusion criteria):	Individuals aged 12 and above who are new users of antidepressants, with new diagnosis of MDD, in the period between 1 st of January 2013 and 31 st of December 2022 (or the latest available date if earlier), with at least 1 year of data visibility prior they become eligible for study inclusion.
Exposure:	Antidepressants: 
 
• Non-selective monoamine reuptake inhibitors
 
• Selective serotonin reuptake inhibitors
 
• Other Antidepressants (excluding esketamine and hyperici herba)
 

Comparator:	None
Outcome:	None
Time (when follow up begins and ends):	Follow-up will start on the date of the first prescription and/or dispensation of the antidepressant class of interest (index date) until the earliest of loss to follow-up, end of data availability or death, or end of study period (31st December 2022).

	D2.2.3 –Study Protocol for P2 C1-008	
	Author(s): [name], [name]	Version: v3.1 – Final
		Dissemination level: public

Setting:	Inpatient and outpatient setting using data from the following 5 data sources: CPRD GOLD (UK), IQVIA DA Germany (Germany), IMASIS (Spain), IPCI (the Netherlands) and SIDIAP (Spain).
Main measure of effect:	Duration summary descriptive statistics (mean, median, quantiles 25% and 75%, minimum and maximum) of antidepressant use, patient level drug utilisation to assess duration of use of the first exposure episode of the respective antidepressant class of interest.

	D2.2.3 –Study Protocol for P2 C1-008	
	Author(s): [name], [name]	Version: v3.1 – Final
		Dissemination level: public

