### 8.3 Study Period

The study period will be from 1st of January 2013 to 31st December 2022 or the end of available data in each of the data sources if earlier (see Table 4 for more details).

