### 8.4 Follow-up

Patient-level characterisation: study participants will be followed from the date of MDD diagnosis (index date) until the earliest of loss to follow-up, end of data availability, death, or end of study period (31st December 2022). Additionally:

- To assess the proportions of patients with newly diagnosed MDD initiating antidepressant therapy, incident MDD cases will be followed from the date of MDD diagnosis (index date) until the first prescription of the antidepressant class of interest, up to 24 weeks following MDD diagnosis.
- To assess the proportions of patients with newly diagnosed MDD switching or discontinuing specific antidepressant therapy, incident MDD cases on antidepressant therapy will be followed from the date of the first prescription of the specific antidepressant class of interest up to the date of specific intervals (4, 6, 8, 12, and 24 weeks) after starting antidepressant therapy.
- To assess the proportions of patients with newly diagnosed MDD starting, switching and discontinuing concomitant therapy with psycholeptics, incident MDD cases on antidepressant therapy will be followed from the date of the first prescription of the specific antidepressant class of interest up to the date of specific intervals (4, 6, 8, 12, and 24 weeks) after starting antidepressant therapy.

Patient-level utilization of antidepressants: study participants will be followed up from the date of incident prescription and/or dispensation of antidepressant class of interest (index date) until the earliest of loss to follow-up, end of data availability, death, or end of study period (31st December 2022).

	D2.2.3 –Study Protocol for P2 C1-008	
	Author(s): [name], [name]	Version: v3.0 – Revised
	Dissemination level: Confidential	

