## 8.8 Data analysis

**Table 11.** Description of Study Types and Type of analysis

STUDY TYPE	STUDY CLASSIFICATION	TYPE OF ANALYSIS
Disease Epidemiology - Patient Level Characterisation	Off-the-shelf (C1)	
 
- Percentage of patients initiating treatment with specific antidepressants or psycholeptics
 
- Percentage of patients switching treatment to specific antidepressants or psycholeptics
 
- Percentage of patients discontinuing treatment with specific antidepressants or psycholeptics
 

Patient Level DUS	Off-the-shelf (C1)	
 
- Estimation of the mean, median, 25th percentile, 75th percentile, minimum, and maximum durations of antidepressant use.
 
- Estimation of the median, 25th percentile, 75th percentile, minimum, and maximum of the drug quantity at first prescription of the antidepressant of interest
 

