#### Patient-level characterisation: Duration of antidepressant use

The calculation of individual prescription/dispensing durations (in days) will be derived from the DRUG\_EXPOSURE table within the CDM. This table contains the drug\_exposure\_start\_date and the drug\_exposure\_end\_date, which are populated during the Extraction Transform and Load (ETL) process based on available source data. The advantage of this approach is that the drug exposure duration is directly obtained, eliminating the need to infer it from other information during analysis. This ensures a consistent analytical pipeline across all databases. New users will be selected based on their first prescription of the respective antidepressant class of interest after the start of the study. For each patient, at least 1 year of data visibility will be required prior to that prescription. New users will be required to not have been exposed to the drug of interest for at least 1 year prior the current prescription. If the start date of a prescription does not fulfil the exposure washout criteria of 1 year of no use, the whole exposure is eliminated.

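### Objective 2 summarises first-era antidepressant duration as if every era had ended, so eras still open at loss, end of data or 31 December 2022 bias it downward

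*Protocol*

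**What the plan says.** - **Estimator.** Table 11 in section 8.8 lists, for the patient-level utilisation study, "Estimation of the mean, median, 25th percentile, 75th percentile, minimum, and maximum durations of antidepressant use". Table 2, part B gives the same as the main measure: "Duration summary descriptive statistics (mean, median, quantiles 25% and 75%, minimum and maximum) of antidepressant use". The abstract (Data analyses, Objective 2) fixes the episode: duration "of antidepressant use in patients with newly diagnosed MDD during the first treatment era will be estimated".
- **Entry.** Section 8.3: "The study period will be from 1st of January 2013 to 31st December 2022 or the end of available data". Section 8.5.2 and the duration paragraph of 8.8.3 require one year of visibility and one year without use before the first prescription. Neither requires any follow-up after it.
- **End of follow-up.** Section 8.4 follows new users "until the earliest of loss to follow-up, end of data availability, death, or end of study period"; Table 2, part B agrees.
- **Source of duration.** Section 8.8.3 takes start and end dates from the drug exposure table and says "The advantage of this approach is that the drug exposure duration is directly obtained, eliminating the need to infer it from other information during analysis". Eras separated by 7 days or less are merged.
- **Loss to follow-up.** Section 11 restricts to patients with enough follow-up, but only in the treatment-pattern analysis. The sensitivity analysis in 8.8.4 concerns dropout between weeks 4 and 24, and runs only if more than half have dropped out. The limitations on duration in section 11 are prescribed versus actual use and missing quantity or dosing.

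**The concern.** An era still running when observation stops is known only to have lasted at least that long. A plain mean or quantile treats it as complete, and nothing in the protocol flags, counts or models such eras. Someone who starts in December 2022 can contribute at most a few weeks of observed follow-up, however long treatment continues.

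Reading dates directly from the drug exposure table does not help, because prescriptions written after the end of observation are not in it.

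Results are reported by database, and observation differs between them. Section 8.2 gives a median follow-up of 4.7 years for IPCI and a mean of 15 years for SIDIAP. In IQVIA DA Germany observation ends at the last consultation. Identical prescribing could therefore yield different reported durations, in a study meant to show how far trial experience carries over to practice.

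**Working it through.** The protocol states no duration or follow-up calculation to reproduce, so the direction is argued from the text and the size is shown over a range.

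**Direction.** Let T be the true first-era duration and C the time from first prescription to loss, end of data or 31 December 2022. The planned summary describes X = min(T, C), which is never longer than T. If end dates are not clipped at the end of observation, the era stops at the end of the last recorded supply. That softens the cut by at most part of one prescription and does not remove it.

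**Inputs.**
- Entry uniform over 2013–2022: 10 × 365 + 2 = 3,652 days (assumed uniform).
- Loss: IPCI's median follow-up of 4.7 years less the 1-year look-back = 3.7 years, or 3.7 × 365.25 = 1,351 days; exponential and independent of T (assumption).
- T lognormal with median m and log-scale SD σ (assumption; no durations are given).

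**Formula.** The median of X is the t that solves P(T > t) × P(C > t) = 0.5, where P(T > t) = 1 − Φ(ln(t/m)/σ). P(C > t) is 1 − t/3652 for the administrative cut, multiplied by 2^(−t/1351) when loss is added.

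**Example, m = 180, σ = 1.5.**
- Administrative cut only, t = 165: ln(165/180)/1.5 = −0.058, so P(T > t) = 0.523; 1 − 165/3652 = 0.955; product 0.50.
- Loss added, t = 143: 0.561 × 0.961 × 0.929 = 0.50.

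**Results.** Each pair is administrative cut only / with loss. Means and open eras come from a simulation of 1,000,000 draws per row; median percentages use unrounded values.

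| True median, days (σ) | Planned median | Median understated, % | Mean understated, % | Eras open, % |
|---|---|---|---|---|
| 30 (1.0) | 29.7 / 29.1 | 1.0 / 2.9 | 2 / 5 | 1 / 4 |
| 60 (1.0) | 58.8 / 56.7 | 2.0 / 5.6 | 4 / 9 | 3 / 7 |
| 90 (1.2) | 86.8 / 81.4 | 3.6 / 9.5 | 10 / 20 | 5 / 12 |
| 180 (1.5) | 164.7 / 143.4 | 8.5 / 20.3 | 35 / 49 | 13 / 24 |

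In the last row the upper quartile falls from 495 to 425 / 348 days. Kaplan-Meier on the same draws returned the true median to within half a day in every row, because loss was independent by construction.

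**Other shape.** Exponential durations with loss at a median of 4.7 years give medians understated by 6% (true 60 days) and 15% (true 180 days); with the administrative cut alone, 2% and 7%.

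**How severe is the loss scenario?** Combined with the administrative cut, median potential follow-up solves (1 − t/10) × 2^(−t/3.7) = 0.5. At t = 2.3 years: 0.77 × 0.65 = 0.50. That is below 3.7 years, so for IPCI the second figure of each pair is on the severe side.

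**When Kaplan-Meier fails.** Assume 30-day prescriptions, a true median of 120 days, and 30% of patients whose last consultation is their final prescription visit, with the era clipped and censored there. Kaplan-Meier then gave 150 days (lognormal) or 180 days (geometric).

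**The case against.** The strongest reply is that this is a secondary objective in a descriptive study with no hypothesis, comparator or meta-analysis, and that observed duration is a legitimate summary if it is called that. First eras within one class, joined only across gaps of 7 days or less, may also be short, and then the bias is a few percent. Both points stand. They lower the priority and widen the range, but the plan does not label the result as observed duration, and without a count of open eras nobody could tell whether the benign case applies.

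Nor is this a detail left to an analysis plan: the protocol itself names the estimator three times.

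A second reply is that Kaplan-Meier brings its own error where observation ends at the last consultation. This also stands: someone who stops and does not return looks censored, and the estimate can overshoot. It is a reason to show both estimates, not to rely on the raw one alone.

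A reader might infer that death is one of the truncating events, because section 8.4 lists it with the others. It is not: use ends at death, so that duration is complete.

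**Conclusion.** The point holds. Eras open at loss, end of data or 31 December 2022 are counted as finished, so mean, median, upper quartile and maximum are biased downward. The lower quartile is affected less in days and the minimum hardly at all. The direction follows from the text. The size does not: about 1–3% of the median at a true 30 days up to 8–20% at 180 days with a heavy tail, more for the mean, under assumed lognormal durations, uniform entry and independent loss.

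Three stronger readings are tempting but unsupported:
- That truncation is worst in IQVIA DA Germany. Section 8.2 says how observation ends there but gives no follow-up length.
- That the median is off by much more than a fifth. This needs faster loss or longer eras than anything the documents state.
- That the intercurrent-event proportions at weeks 4 to 24 share the defect. They are restricted to patients with sufficient follow-up and are a separate analysis.

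For a secondary descriptive objective this should be fixed; it does not undermine the study.

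**What to change.** In Table 11 and section 8.8.3:

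1. Report, by class and database, the number and percentage of first eras open at the end of observation. Given the 7-day joining rule, an era that ends within 7 days of that date, or beyond it, cannot be known to have ended.
2. Add Kaplan-Meier median and quartiles and a restricted mean over a fixed horizon (for example 24 weeks and 1 year). Treat eras open at loss, end of data or 31 December 2022 as censored, and count death as an end of use.
3. Keep the raw mean, quartiles, minimum and maximum, labelled as observed duration.
4. For IQVIA DA Germany, state that censoring may be related to stopping treatment and show the raw and Kaplan-Meier estimates side by side.
5. Add truncation to the duration limitations in section 11.

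The cost is a few sentences and a little local code; section 8.8.4 already accepts an analysis that the treatment-pattern package cannot produce. The downsides are that an upper quartile may not be reached where follow-up is short, and that Kaplan-Meier may overstate duration where censoring is informative.

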### 8.8.1 Federated Network Analyses

Analyses will be conducted separately for each database. Before study initiation, test runs of the analytics are performed on a subset of the data sources or on a simulated set of patients and quality control checks are performed. Once all the tests are passed, the final package is released in the version-controlled Study Repository for execution against all the participating data sources. pa

The data partners locally execute the analytics against the OMOP-CDM in R Studio and review and approve the by default aggregated results before returning them to the Coordination Centre. Sometimes multiple execution iterations are performed, and additional fine tuning of the code base is needed. A service desk will be available during the study execution for support.

The study results of all data sources are checked after which they are made available to the team in the Digital Research Environment (DRE) and the Study Dissemination Phase can start. All results are locked and timestamped for reproducibility and transparency.

### 8.8.2 Patient privacy protection

	D2.2.3 –Study Protocol for P2 C1-008	
	Author(s): [name], [name]	Version: v3.1 – Final
		Dissemination level: public

Cell suppression will be applied as required by databases to protect people’s privacy. Cell counts < 5 will be masked.

### 8.8.3 Statistical model specification and assumptions of the analytical approach considered

#### R-packages

We will utilize the R packages "TreatmentPatterns" for patient-level treatment characterizations and "DrugUtilization" for patient-level drug utilization analyses.

#### Patient-level characterisation: Treatment initiation, switching, and discontinuation

To characterise treatment of MDD, the number and percentages of patients receiving each of a pre-specified list of MDD treatments (as listed in section 8.6.1) will be described at index date, and 4, 6, 8, 12, and 24 weeks post index date. The criteria for treatment switching and discontinuation will be based on the options currently available in the standard analytical tools that will be used in this project, specifically, the “TreatmentPattern” R package. This analysis will produce sunburst plots and Sankey diagrams to describe treatment initiation, switching and discontinuation over time (objectives 1 and 3).

#### Patient-level characterisation: Duration of antidepressant use

The calculation of individual prescription/dispensing durations (in days) will be derived from the DRUG\_EXPOSURE table within the CDM. This table contains the drug\_exposure\_start\_date and the drug\_exposure\_end\_date, which are populated during the Extraction Transform and Load (ETL) process based on available source data. The advantage of this approach is that the drug exposure duration is directly obtained, eliminating the need to infer it from other information during analysis. This ensures a consistent analytical pipeline across all databases. New users will be selected based on their first prescription of the respective antidepressant class of interest after the start of the study. For each patient, at least 1 year of data visibility will be required prior to that prescription. New users will be required to not have been exposed to the drug of interest for at least 1 year prior the current prescription. If the start date of a prescription does not fulfil the exposure washout criteria of 1 year of no use, the whole exposure is eliminated.

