##### Study objectives

1. To examine the proportion of patients with newly diagnosed major depressive disorder who start treatment with antidepressants (NSRIs, SSRIs, or other anti-depressants), and of those the proportion who switch or discontinue treatment by specific timepoints (4, 6, 8, 12, and 24 weeks after treatment initiation), stratified by age group, sex, and country/database during the study period (2013 - 2022).
2. To estimate the duration of antidepressant use in patients with newly diagnosed major depressive disorder who initiate treatment with antidepressants (NSRIs, SSRIs, or other antidepressants), stratified by age group, sex, and country/database during the study period (2013 - 2022).
3. To assess the proportions of patients with newly diagnosed major depressive disorder who initiate, switch, or discontinue treatment with psycholeptics (antipsychotics, anxiolytics, hypnotics, and sedatives) by specific timepoints (4, 6, 8, 12, and 24 weeks) after starting antidepressant therapy, stratified by age group, sex, and country/database during the study period (2013 - 2022).

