**Table 5: Operational Definition of Time 0 (index date) and other primary time anchors**

Study population name(s)	Time Anchor Description (e.g., time 0)	Number of entries	Type of entry	Washout window	Care Setting 	Code Type 	Diagnosis position	Incident with respect to...	Measurement characteristics / validation	Source of algorithm
All patients from the database eligible for the study and newly diagnosed with MDD	Patient present in the database during the study period (2013-2022) and with at least 1 year of valid database history, and no record MDD diagnosis in the previous year.	Single entry	Incident	[-365, ID]	IP and OP	n/a	n/a	MDD	n/a	n/a
All patients from the database eligible for the study – Analysis of incident antidepressant use in patients with newly diagnosed MDD	Patient present in the database during the study period (2013-2022) and with at least 1 year of valid database history.	Single entry	Incident	[-365, ID]	IP and OP	n/a	n/a	Specific drug class	n/a	n/a

ID = index date, IP = inpatient, OP = outpatient, n/a = not applicable, MDD = Major Depressive Disorder

	D2.2.3 –Study Protocol for P2 C1-008	
	Author(s): [name], [name]	Version: v3.0 – Revised
		Dissemination level: Confidential

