### 8.5.2 Patient-level utilization of antidepressants

All individuals aged 12 and above who are new users of antidepressants with incident MDD diagnosis, after 1 year of no use of the specific medication, in the period between 1st of January 2013 and 31st of December 2022 (or latest date available), with at least 1 year of data visibility prior to the date of their first prescription of the antidepressant class of interest.

	D2.2.3 –Study Protocol for P2 C1-008	
	Author(s): [name], [name]	Version: v3.0 – Revised
	Dissemination level: Confidential	

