#### Drug exposure calculations

Drug eras will be defined as follows: Exposure starts at date of the first prescription after the first MDD diagnosis. For each prescription, the estimated duration of use is retrieved from the drug exposure table in the CDM. Subsequent prescriptions for the same drug will be combined into continuous exposed episodes (drug eras) using the following specifications:

Two drug eras will be merged into one continuous drug era if the distance in days between end of the first era and start of the second era is  $\leq 7$  days. The time between the two joined eras will be considered as exposed to the first era as show in in Figure 1.

	D2.2.3 –Study Protocol for P2 C1-008	
	Author(s): [name], [name]	Version: v3.1 – Final
	Dissemination level: public	

[figure not shown]

Gap era joint mode	Schematics	Dose in between	Cumulative dose	Cumulative time
“first”		$d_1$	$d_1 \cdot (x_1 + x_{12}) + d_2 \cdot x_2$	$x_1 + x_{12} + x_2$
“second”		$d_2$	$d_1 \cdot x_1 + d_2 \cdot (x_2 + x_{12})$	$x_1 + x_{12} + x_2$
“zero”		0	$d_1 \cdot x_1 + d_2 \cdot x_2$	$x_1 + x_{12} + x_2$
“join”		NA	$d_1 \cdot x_1 + d_2 \cdot x_2$	$x_1 + x_2$

[figure not shown]

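### For Objective 2 the protocol gives two incompatible rules for the index prescription, one anchored at study start and one at the MDD diagnosis

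*Protocol*

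**What the plan says.** Section 8.8.3 contains both rules for Objective 2. Under the heading on duration of antidepressant use: "New users will be selected based on their first prescription of the respective antidepressant class of interest after the start of the study". That text also requires one year of data before the prescription and one year without the drug. An exposure whose start fails the washout is eliminated as a whole. Under drug exposure calculations: "Exposure starts at date of the first prescription after the first MDD diagnosis".

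The other definitions of the Objective 2 cohort do not settle the order:

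- Abstract, Data analyses: "The index date will be determined as the date of the first prescription of the specific antidepressant class for each individual".
- Section 8.5.2: "All individuals aged 12 and above who are new users of antidepressants with incident MDD diagnosis", followed by the one-year washout and the study dates.
- Table 2B: new users with a new MDD diagnosis in 2013 to 2022, followed from the first prescription or dispensing of the class.
- Table 5, second row, "Analysis of incident antidepressant use in patients with newly diagnosed MDD": presence in the database in 2013 to 2022 and one year of history.

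For the initiation outcome, section 8.4 does set an upper limit. Patients are followed from diagnosis "until the first prescription of the antidepressant class of interest, up to 24 weeks following MDD diagnosis". Its second and third bullets (switching, discontinuation, psycholeptics) start at the first prescription of the class and do not repeat the limit. Objective 1 in the Abstract links the two steps: "and of those the proportion who switch or discontinue treatment by specific timepoints".

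**The concern.** The study is meant to describe treatment of newly diagnosed MDD so that it can be set against trial patients. An antidepressant era that began before the diagnosis may belong to another indication or to an earlier, uncoded problem, and its length need not resemble first treatment of the new diagnosis. If the study-start rule is coded, such eras enter the Objective 2 durations. If the diagnosis rule is coded, some of the same patients leave the cohort altogether. All five databases run one code package, so whichever sentence the programmer follows fixes the result everywhere, and a reader of the report could not tell from the protocol which cohort was analysed.

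**Working it through.** No sample size, power or alpha is involved, and the protocol states no figure to reproduce. The check sets the rules side by side, follows example patients through them, and adds one piece of date arithmetic.

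**1. The two rules**

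- Rule A (section 8.8.3, duration of use): index = first prescription of the class after study start. The diagnosis date plays no part.
- Rule B (section 8.8.3, drug exposure calculations): exposure starts at the first prescription after the first MDD diagnosis. Only a lower bound is given.
- Washout (section 8.8.3): one year without the drug before the prescription, otherwise the whole exposure is removed.

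**2. Patients under each rule** (all assumed to have the required year of data)

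- *First use of the class falls after diagnosis.* A and B pick the same prescription.
- *Class started within the year before diagnosis and continued.* Under A the pre-diagnosis prescription is the index, it can pass the washout, and the era is counted from that date. Under B the first post-diagnosis prescription is the start. The patient was exposed in the preceding year, so the washout fails and the exposure is removed.
- *Class prescribed in 2014, MDD first diagnosed in 2019.* Under A the 2014 era is reported as use in newly diagnosed MDD. Under B the 2014 era is ignored. The patient contributes a later era only if the class is prescribed again after the diagnosis and that prescription passes the washout.

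So the rules agree for the first type of patient and give different cohorts and durations for the other two.

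**3. Do other provisions decide?** The Abstract, section 8.5.2, Table 2B and Table 5 require both a new user and a new diagnosis, but give neither order nor interval. They fit A and B equally.

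**4. Pathway analyses (Objectives 1 and 3).** Table 2A and section 8.4 start follow-up at diagnosis, and the TreatmentPatterns parameter table sets periodPriorToIndex to 0 days. Pre-diagnosis starts are therefore kept out. That parameter does not govern Objective 2, which uses the DrugUtilization package.

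**5. Outer limit of the gap**

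- 1 January 2013 to 31 December 2022 = 10 × 365 + 2 leap days − 1 = 3,651 days; 3,651 / 7 = 521.6 weeks.
- Initiation window: 24 × 7 = 168 days.
- Ratio: 3,651 / 168 = 21.7.

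The 3,651 days bound the gap before diagnosis under A, and the gap after diagnosis under either rule. They are the length of the study period, not an expected interval.

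**The case against.** The strongest defence is that the two sentences do different jobs: the first is a study-period and washout filter, and the second says when exposure begins. On that reading the 2014 era in the example is never counted. The reading is possible, but the text does not state it, and it does not restore a single rule. The washout would be checked on one prescription and the duration measured from another. The patient who started shortly before diagnosis would then stay in with the early part of the era cut off, a third result that matches neither rule coded alone. The need to reconcile the sentences stands.

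Three stronger readings are tempting, and the documents do not support them:

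- A reader might infer that pre-diagnosis prescriptions contaminate all the analyses. Follow-up from diagnosis and the zero lookback exclude them from the switching, discontinuation and psycholeptic pathways.
- A reader might infer that switching and discontinuation are measured in a different group from the counted initiators. The nesting phrase in the Abstract objectives and in Table 2A, and the order of the Abstract's data-analysis text, point to the 24-week initiators. Section 7 words Objective 1 more loosely, and the second and third bullets of section 8.4 omit the cap, so this is an ambiguity and not a proven mismatch.
- A reader might infer that late starters do not belong in Objective 2. That objective promises no window and enters patients per class. A hard 24-week cut would drop a patient who moves to a second class later, or whose first drug treatment follows a period of psychotherapy, which section 6 names as part of management. The absence of a cap there is a defensible choice.

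**Conclusion.** The contradiction is real and confined to the Objective 2 index prescription. Followed literally, the study-start rule admits pre-diagnosis prescriptions as treatment of newly diagnosed MDD, while the diagnosis rule removes patients who began the class in the year before diagnosis and continued. The conclusion rests on reading the two sentences of section 8.8.3 as written, and on no other section stating the order.

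The size of the effect cannot be computed, because the protocol gives no distribution of the interval between diagnosis and prescription. The dates show only what is permitted: up to 3,651 days, against 168 days for the initiation outcome. Any share of early or late starters would rest wholly on assumed inputs. The missing upper limit in the second and third bullets of section 8.4 needs a clarifying sentence and is not an error in itself.

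**What to change.** 1. In section 8.8.3, duration of use, replace the study-start anchor with: first prescription of the class on or after the MDD diagnosis date, within the study period. Apply the one-year washout to that prescription. Match the sentence under drug exposure calculations, so that a prescription on the day of diagnosis is clearly included.
2. Carry the same rule into section 8.5.2, Table 2B and the second row of Table 5.
3. In the second and third bullets of section 8.4, state that the antidepressant starters are those counted by the initiation outcome, that is, within 24 weeks of diagnosis.
4. Set no hard cap for Objective 2. Report duration separately for starts within 24 weeks of diagnosis and for later starts.

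The cost is protocol wording, one date condition in the cohort code, slightly more tabulation, and smaller strata for the less-used classes, where more cells may fall below the minimum count of 5. Patients who began the class in the year before diagnosis leave the Objective 2 cohort. Reporting their number would show how much the choice of anchor matters.
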